#### Galveston Orientation and Amnesia Test

This measure is administered and scored in the same way as described in the TRACK-TBI Outcomes Assessment SOP. The GOAT measure is administered at the beginning of the assessment to determine if the Abbreviated Assessment Battery should be administered and whether to administer the CAP and/or CRS-R. This measure can also be administered at any point during the phone or in-person assessment, if the study coordinator has any concerns about the participant's capacity to consent and complete an assessment.

#### 9.2 Interviews

#### Participant Interview

This interview is administered and responses recorded in the same way as described in the TRACK-TBI Outcomes Assessment SOP for the Participant/Surrogate Interview. The TRACK-TBI Precision Medicine participant interview is based on the TRACK-TBI 3M follow-up Participant Interview and adds a neurologic screen for epilepsy as well as questions pertaining to the impact of the COVID-19 pandemic. The Covid-19 survey questions will assess the impact COVID-19 had or is having on the participant and/or someone close to the participant. The Participant Interview should be administered by telephone but can also be administered in-person if permitted by local policy and acceptable to the subject or LAR.

## 9.3 Measures of Daily/Global Function

## Functional Status Exam (FSE)

The FSE measures change in functional status specifically due to traumatic injury. The measure can be administered in relation to changes due to TBI only or both the changes associated with TBI and peripheral injuries. This measure covers 7 areas of functioning: personal care, ambulation, mobility, major activities (i.e.,

work, school), home management, leisure and recreation and social integration. These areas are evaluated using the concept of dependency to operationally define outcome at four levels. The first level signifies no change, the second level signifies difficulty in performing the activity although the person is still independent, the third level signifies dependence on others some of the time, and the fourth level signifies non-performance or inability to perform the activity or total dependence on others. A total score is generated by summing scores from the 7 categories, yielding a range from 0 (return to pre-injury baseline in all areas) to 21 (total dependence on others or can no longer perform any activities across functional areas). Persons who die are assigned a total score of 22. This measure will also be collected from the surrogate. The FSE measure should be administered by telephone but can also be administered in-person if permitted by local policy and acceptable to the subject or LAR.

Additional information regarding the administration of the FSE can be found in the pdf "Functional Status Examination Manual" saved on the Study Shared BOX folder at "Box\TRACK-TBI Precision Medicine Study Documents\Outcomes Core\Outcomes training and administration guidance".

## Glasgow Outcome Scale- Extended (GOSE)

This measure is administered and scored in the same way as described in the TRACK-TBI Outcomes Assessment SOP. A "TBI" score will be collected for the purposes of TRACK-TBI Precision Medicine. The GOSE should be administered by telephone but can also be administered in-person if permitted by local policy and acceptable to the subject or LAR.

### Scoring the GOSE in Relation to the FSE

There is considerable overlap in the item content of the FSE and GOSE. Because the FSE is administered before the GOSE, the examiner will have extracted information from the subject during administration of the FSE that can be used to score the GOSE. Although it is necessary to independently administer and score *all* the GOSE areas, information obtained during the FSE interview that relates to a specific GOSE area can be directly applied to the GOSE rating. This approach will minimize subject burden and help reduce the completion time of the TRACK-TBI Precision Medicine battery.

#### Standard Assessment of Concussion (SAC)

The Standardized Assessment of Concussion (SAC) is a brief screening instrument designed for the neurocognitive assessment of concussion by a non-neuropsychologist without prior expertise in psychometric testing. The SAC requires approximately 5-10 minutes to administer and includes measures of orientation, immediate memory, concentration, and delayed recall, summing to a total composite score of 30 points, with a higher score indicating better cognitive functioning. The SAC will be obtained only at enrollment and must be collected in-person; the SAC cannot be collected by telephone.

#### **Disability Rating Scale (DRS)**

This measure is administered and scored in the same way as described in the TRACK-TBI Outcomes Assessment SOP. The DRS measure will be administered during the in-person assessments but can be collected by phone. Only the DRS Caregiver version will be collected in this study.

## 9.4 Measures of Psychological Health/Neurobehavioral Symptoms

#### Brief Symptom Inventory 18 (BSI-18)

This measure is administered and scored in the same way as described in the TRACK-TBI Outcomes Assessment SOP. The BSI-18 measure should be administered by telephone but can also be administered inperson if permitted by local policy and acceptable to the subject or LAR.

#### Rivermead Post Concussion Symptoms Questionnaire (RPQ)

This measure is administered and scored in the same way as described in the TRACK-TBI Outcomes Assessment SOP. The RPQ measure should be administered by telephone but can also be administered inperson if permitted by local policy and acceptable to the subject or LAR.

## Posttraumatic Stress Disorder Checklist (PCL-5)

This measure is administered and scored in the same way as described in the TRACK-TBI Outcomes Assessment SOP. The PCL-5 should be administered by telephone but can also be administered in-person if

permitted by local policy and acceptable to the subject or LAR.

## Quality of Life After Brain Injury- Overall Scale (QoLIBRI-OS)

This measure is administered and scored in the same way as described in the TRACK-TBI Outcomes Assessment SOP. The QoLIBRI-OS should be administered by telephone but can also be administered inperson if permitted by local policy and acceptable to the subject or LAR.

## Columbia Suicide Severity Rating Scale (C-SSRS) Screening Version

The Screening Version of the Columbia will be administered if the participant answers >1 on Q#17 of the BSI-18 (this is the same triggering criteria in TRACK-TBI U01). The Screening Version is a shortened form of the original "Baseline" and "Since Last Visit" forms that assesses suicidal ideation and behavior in the last month, and offers helpful triage categories based on severity. If the participant endorses YES on any question considered "Moderate Risk" (i.e., orange level) or "High Risk" (i.e., red level), examiners should proceed to administer the TRACK-TBI Suicide Protocol and Safety Plan (saved on the Study Shared BOX folder at "Box\TRACK-TBI Precision Medicine Study Document\Outcomes Core\Outcomes Core SOP"). The C-SSRS measure will be administered during the in-person assessments but can be collected by phone.

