# TRACK TBI Precision Medicine Flexible Outcome Battery Flow Chart

# 8 TRACK-TBI PRECISION MEDICINE FLEXIBLE OUTCOME ASSESSMENT BATTERY AND ORDER OF ADMINISTRATION

## 8.1 Enrollment Battery (at consent or by phone within 24 hours of injury): ~11 minutes

- 1. Rivermead Post Concussion Symptoms Questionnaire (RPQ): 3 mins
- 2. Brief Symptom Inventory 18 (BSI-18): 3 min
- 3. Standard Assessment of Concussion\* (SAC): 5 min

The enrollment outcome assessment battery will be administered only to participants who score ≥75 on the Galveston Orientation and Amnesia Test (GOAT).

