The FDA has set recommendations for exposure in MRI studies and the proposed 3T examinations satisfy those criteria. The guidelines from the Bureau of Radiological Health of the FDA will be followed in regard to specific absorption rate (SAR) of radiofrequency energy and time varying magnetic fields (dB/dt). Precautions will be maintained so that SAR will be less than 8 watts per kilogram in any 1 gram of tissue. This is the estimated power required to raise the temperature 1 degree centigrade. The maximum dB/dt will be set at 20T/sec for > 120usec or 200T/sec for < 12usec. These levels are well below peripheral nerve stimulation threshold in humans, both children and adults. In rare cases, subjects may still experience some peripheral nerve stimulation during portions of the MRI procedure. These experiences are transient and harmless. MRI participants will be instructed prior to examination to refrain from skin-on-skin contact of their extremities (e.g., clasping hands or legs) to further reduce this risk. The MRI will produce loud noises during image acquisition. The decibel intensity of these noises is not considered harmful per FDA regulations, and is below FDA guidelines of 140 dB peak referenced to 20 micropascals. Subject will be provided with earplugs and noise-cancelling headphones/earpads to minimize discomfort.

Subjects will always be in communication with the MRI technologist and will be given a squeeze ball that triggers an alarm. If the subject indicates at any point that they have a desire to stop the procedure, the exam will be terminated immediately and without any penalties to the subject in any way.

If any unexpected findings are identified that may be clinically significant, the participant will be counseled by the Site PI and recommended to seek medical care from their primary care physician.

**Outcomes.** Some of the questionnaires and interviews used in this research ask about personal and potentially sensitive information. This will be explained to subjects both orally and in the consent document. Further, only trained study personnel who are sensitive to these issues will administer such interviews and questionnaires. If a subject endorses any of the questions regarding suicide, it will be documented in the research record and the study staff will follow the **TRACK-TBI Suicide Protocol and Safety Plan** (saved on the Study Shared Box folder at: BoxTRACK-TBI Precision Medicine Study Documents\Outcomes Core\Outcomes Core SOP).

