assessments are completed and checking for data quality monitoring purposes is completed, PHI for the subject will no longer be accessible to previously authorized personnel except the study site PI. At project conclusion, PHI data will be stored in a password protected PDF file and given to the site PI for long-term protected storage. The QuesGen Data Manager will then remove the PHI data from all server hard drives and all backup devices. QuesGen will not retain any copies of the PHI data long-term. These identifiers will then be accessible only by the study site PI and would be used at a later time only if it becomes necessary to contact the subject for additional studies or for regulatory purposes.

**Biospecimens.** For the blood draw, no more than two venipuncture attempts will be performed and specimens will be coded when the draw is complete.

**Neuroimaging.** As noted, the total scan time is approximately 60-75 minutes during which time the subject will have continuous communication with the experimenter. Some patients find the loudness of the oscillating gradients during image acquisition to be discomforting, but the acoustical noise level is below FDA guidelines of 140 dB peak referenced to 20 micropascals. In addition, all patients are provided with earplugs to reduce the noise. There is no evidence for long-term negative effects of MRI procedures on the body. The 3T scanner is an FDA-approved system. For patients' safety, only MRI-compatible monitoring equipment will be used in the scanner suite for any patients requiring that for the ultra-early MRI.

**Outcomes.** An experienced outcomes team designated by the Outcomes Core will train all outcomes personnel for TRACK-TBI. Only trained study personnel sensitive to the inherent issues across cognitive, mental health, psychological, and quality of life domains will administer the outcome instruments for the study. Subjects will be re-introduced to the study at each outcomes time point for understanding and approval to continue participation. Subjects are informed that they are free to not answer any question that may be uncomfortable for them. If a subject endorses any of the questions regarding suicide, it will be documented in the research record and the research personnel will notify the Site PI and activate local suicidality protocols.

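### Sections 9.4, 12.1 and 12.2 state three inconsistent suicidality rules, so an answer that calls for action in one section calls for none in another

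*Protocol*

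**What the plan says.** Section 9.4 (C-SSRS Screening Version) has two steps. The screen "will be administered if the participant answers >1 on Q#17 of the BSI-18". After that, only a YES on a question classed as Moderate or High Risk leads on, and then "examiners should proceed to administer the TRACK-TBI Suicide Protocol and Safety Plan". The section says nothing about what follows a YES on a question below those two levels, or an item 17 answer that does not exceed 1.

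Section 12.1 (Outcomes paragraph) has one step and no threshold: "If a subject endorses any of the questions regarding suicide", the fact is recorded and staff follow the same study Plan.

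Section 12.2 (Outcomes paragraph) opens with the same condition and also requires a record, but then "the research personnel will notify the Site PI and activate local suicidality protocols". It does not mention the Plan.

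Two other places bear on this. The table in section 8.2 lists the C-SSRS as given when needed, with a footnote that the BSI-18 triggers it and no threshold. The enrolment battery in section 8.1 includes the BSI-18 ("Brief Symptom Inventory 18 (BSI-18): 3 min") but does not list the C-SSRS.

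**The concern.** All three sections tell site staff what to do when a participant indicates suicidal thoughts, and all three are written as instructions. Section 9.4 is what an examiner would consult when giving the instrument. Sections 12.1 and 12.2 describe the risks of the outcome assessments and the protections against them. If the instrument section acts on fewer answers than the protection sections describe, participants may not receive the protection the protocol says they have. With five sites, staff working from different sections could handle the same answer differently, and each could point to protocol text in support. At stake is a missed or inconsistent response to a safety signal, not the statistical analysis.

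**Working it through.** The protocol gives no figure to reproduce, so the check is a side-by-side reading of the rules.

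| Section | What sets the rule off | What staff then do |
|---|---|---|
| 9.4 | BSI-18 item 17 above 1, then YES on a Moderate or High Risk C-SSRS question | Study Plan |
| 12.1 | Any suicide question endorsed | Record; study Plan |
| 12.2 | Any suicide question endorsed | Record; notify Site PI; local protocols |

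**Count.** Sections 12.1 and 12.2 share one trigger, and 9.4 has another: two triggers. Sections 9.4 and 12.1 share one response, and 12.2 has another: two responses. The trigger-response pair differs in each section: three rules.

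**Case A: item 17 above 1, and YES only on a C-SSRS question below Moderate Risk.**
- Under 9.4 the screen is given, but no further step is stated.
- Under 12.1 a suicide question has been endorsed, so the Plan starts.
- Under 12.2 the Site PI is notified and local protocols are activated.
- This case does not depend on how the BSI-18 is coded. It assumes that the screen has a level below Moderate. Section 9.4 points that way: it speaks of triage categories by severity and names only two of them as leading to the Plan.

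**Case B: item 17 answered 1.**
- Under 9.4 the answer is not above 1, so no screen is triggered and no action is stated.
- Under 12.1 and 12.2 the outcome depends on whether 1 counts as endorsement. The BSI-18 entry in section 9.4 leaves administration and scoring to the TRACK-TBI Outcomes Assessment SOP, and the protocol does not print the response scale.
- If the lowest option is coded 0, an answer of 1 is an endorsement and the sections diverge. If the lowest option is coded 1, an answer of 1 is no endorsement, the item 17 threshold means any endorsement, and the first step of 9.4 agrees with section 12.

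**Case C: YES on a Moderate or High Risk question.**
- All three sections call for action, so the triggers agree.
- Sections 9.4 and 12.1 name the Plan; 12.2 names Site PI notification and local protocols and does not say how these relate to the Plan.

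**Enrolment.** The trigger in 9.4 is tied to a BSI-18 item and not to a visit, so on its face it covers the enrolment BSI-18. Section 8.1 lists the BSI-18 without the C-SSRS, even as an instrument to be used when needed, whereas 8.2 does list it that way. The two can be read together, but the protocol does not say so.

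**The case against.** The strongest reply is that these are layers of one procedure. Section 9.4 says when an instrument is given and when the Plan becomes mandatory; it does not say that other answers are ignored. Staff who act on any endorsement under 12.1 breach nothing in 9.4. Site PI notification and local protocols may be steps inside the Plan, which is a separate document and is not available here. The two responses are compatible, and staff can do both.

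Part of this stands. The difference in response may narrow or disappear once the Plan is read, and a reader who infers that 12.2 replaces the Plan goes further than the text. The reply does not remove the difference in trigger. Sections 9.4 and 12.1 open the same Plan on different conditions, and the content of the Plan cannot settle that, because the condition determines whether the Plan is opened at all. Silence in 9.4 about lower-risk answers is no contradiction on its own, but beside an explicit instruction in 12.1 and 12.2 it leaves an examiner working from section 9 without the step that section 12 requires.

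Four stronger readings are tempting, and the document does not support them:
- **Three separate triggers and three separate responses.** There are two of each.
- **An answer of 1 on item 17 is certainly mishandled.** That depends on coding the protocol does not give.
- **The enrolment BSI-18 has no suicide follow-up.** The 9.4 trigger is not restricted to follow-up visits, and 9.4 allows the C-SSRS by phone. The gap is one of confirmation.
- **Every BSI-18 administration is affected, so visits times participants gives the size.** Only certain answers diverge. The enrolment battery is given only at a GOAT score of at least 75 (8.1), the Abbreviated Battery contains no BSI-18 (8.3), and the protocol gives no response frequencies.

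**Conclusion.** The inconsistency is real and lies within the protocol itself. The firm part is the trigger: for a participant whose only positive C-SSRS answer is below Moderate Risk, 12.1 and 12.2 require action and 9.4 states none. This rests on one assumption, that the screen has such a level, which the wording of 9.4 implies. The item 17 part is conditional on 1 counting as endorsement. The response part is an unexplained difference between 12.2 and the other two sections, which the Plan might resolve. No count of affected participants can be derived from the document, and none is needed: the point is that written safety instructions disagree about the same answer. It should be corrected on patient-safety grounds. Which threshold or response is right is not judged here.

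**What to change.** Reconcile sections 9.4, 12.1 and 12.2 to a single trigger and a single response pathway, set out in full in one place, with the other two sections referring to it. The text should:
- define what counts as endorsing a suicide question, including whether a BSI-18 item 17 answer alone does so, and give the item's response scale so that the threshold can be read without the SOP;
- state what happens after a YES on a C-SSRS question below Moderate Risk;
- say how Site PI notification and local protocols relate to the TRACK-TBI Plan;
- confirm that the pathway covers the enrolment BSI-18, including by phone, with a note in section 8.1 that the C-SSRS may be triggered there.

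The clinical team must decide the threshold and the response. The cost is a wording amendment through the single IRB and a short training note to examiners at the five sites. Design, sample size and analysis do not change.

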## 9.5 Measure of Symptom Validity

## Structured Inventory of Malingered Symptomatology (SIMS)

The Structured Inventory of Malingered Symptomatology™ (SIMS™) is a 75-item, true-or-false screening instrument that assesses both malingered psychopathology and neuropsychological symptoms. It is a multiaxial, self-administered measure developed to serve as a screening tool for the detection of feigned or exaggerated psychiatric disturbance and cognitive dysfunction among adults ages 18 years and older across a variety of clinical and forensic settings. The SIMS consists of 75 items that yield a summary score reflective of a general feigning presentation (Total score), as well as five nonoverlapping scales that reflect theoretical and statistical considerations of the more commonly feigned or exaggerated disorders: (a) Psychosis, (b) Neurologic Impairment, (c) Amnestic Disorders, (d) Low Intelligence, and (e) Affective Disorders. The SIMS is intended to serve multiple functions as (a) an initial screening tool for individuals who may not otherwise be referred for specific evaluation of potential feigning within a forensic or medico-legal context or setting; (b) an initial screening tool for individuals suspected of feigning to determine the need for more extensive evaluation; and (c) convergent data in a comprehensive evaluation for potential feigning. The SIMS' brief, easily administered self-report format and fifth-grade reading level reduce clinician burden and allow for completion by a wide range of individuals at varying educational/cognitive levels. The SIMS measure should be administered by telephone but can also be administered in-person if permitted by local policy and acceptable to the subject or LAR.

## 9.6 Measures of Cognitive Performance

#### Rey Auditory Verbal Learning Test (RAVLT)

This measure is administered and scored in the same way as described in the TRACK-TBI Outcomes Assessment SOP, and can only be collected at an in-person assessment. The Delayed Recall trial will be administered after the BSI-18.

#### Trail Making Test

This measure is administered and scored in the same way as described in the TRACK-TBI Outcomes Assessment SOP, and can only be collected at an in-person assessment.

#### Wechsler Adult Intelligence Scale – 4th Edition Processing Speed Index (WAIS-IV) PSI

This measure is administered and scored in the same way as described in the TRACK-TBI Outcomes Assessment SOP, and can only be collected at an in-person assessment.

#### 9.7 Measures of Motor Function

## Finger tapping

The Finger Tapping Test (FTT) measure is one of the most widely used measures of motor functioning While there are several FTTs available, the most popular and well-known administration of this test is as part of the Halstead–Reitan Neuropsychological Test Battery (HRNB). The purpose of this test is to measure the tapping speed of the index finger of each hand. A finger tapping counter device ("key") is provided and should be used for this test. Examinees are instructed to place their hand on the board, allowing only the index finger to move. The base of the hand (not the palm), the thumb and the tips of the other fingers should rest on the board (the hand will be slightly cupped). They then raise and lower the index finger of their dominant hand for five consecutive trials, each lasting 10 seconds, enough to cause the counter on the device to record each tap (or oscillation). This procedure is then repeated for the non-dominant hand, with the requirement that the individual completes five trials within 5-point range. For purposes of this study, two 10-second trials will be given for each hand during the in-person assessment. Total number of finger taps for each trial on each hand should be recorded.

